PROTOCOL

Background

1. Provide the scientific background, rationale and relevance of this project.

Answer/Response:

Transversus Abdominis Plane (TAP) block is a useful tool in pain management after abdominal surgery. It is a regional nerve block that targets T6-L1 thoracolumbar nerves running in the plane between internal oblique and transversus abdominis muscle. It is shown to help with post-operative pain management, reducing pain scores and narcotic pain medication use, as well as promoting earlier return to activity and recovery.^{1,2} TAP block became a very popular, safe, and effective therapeutic adjunct for many different abdominal surgeries ranging from obstetric procedures to general surgery procedures like colorectal surgery.^{3,4} Furthermore, it is used in plastic surgery procedures such as Deep Inferior Epigastric Perforator (DIEP) free flap or Transverse Rectus Abdominis Myocutaneous (TRAM) flap, as they involve extensive amount of abdominal soft tissue incision. Previous studies have shown that TAP block in these procedures significantly reduce post-op pain and narcotic pain medication use.^{5,6} More recently, Exparel (liposomal bupivacaine) has risen to spotlight for providing a longer, sustained local anesthesia. Various surgical disciplines have adopted this agent as part of their pain management protocol. However, there are no literatures that describe the effect of TAP block using Exparel for breast free flap population. We hypothesize that delivering TAP block with Exparel (vs. plain bupivacaine) will provide longer regional blocking effect, hence aiding in pain control and recovery postoperatively.

Objectives/Hypothesis

Answer/Response:

- We hypothesize that liposomal bupivacaine (Exparel) TAP block will provide longer pain control compared to plain bupivacaine TAP block in abdomen-based free flap breast.
- Primary outcome = post-op pain scores during hospitalization, post-op narcotic pain medication use during hospitalization, post-op narcotic pain medication use after discharge (within 30 days of discharge)
- Secondary outcome = Length of stay, Post-op nausea and vomiting (PONV)

Study Design: Biomedical

1. Will controls be used?

Answer/Response: Yes

► IF YES, explain the kind of controls to be used.

Answer/Response: Usual care, TAP block with plain bupivacaine

2. What is the study design?

Answer/Response: Randomized, single-blind control study

3. Does the study involve a placebo?

Answer/Response: No

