Human Participants

Ages: 18 and older

Sex: Female

Race: Any

Subjects- see below

1. Provide target # of subjects (at all sites) needed to complete protocol.

Answer/Response:

100 participants

2. Describe expected rate of screen failure/ dropouts/withdrawals from all sites.

Answer/Response:

Minimal.

Once the patient consents to the study, it is unlikely that they will drop out or withdrawal afterwards given that this is part of a usual care pain management protocol. No extra follow up is required for patients and all the outcomes will be part of a usual post-op data that will be recorded in Epic.

3. How many subjects will be enrolled at all sites?

Answer/Response:

This is a single site study – enrollment at UVA only.

4. How many subjects will sign a consent form under this UVA protocol?

Answer/Response:

All participants (100)

Inclusion/Exclusion Criteria

1. List the criteria for inclusion

Answer/Response:

- All female patients who are 18 years or older who will undergo unilateral or bilateral abdomen-based free flap breast reconstruction at UVA Medical Center from February 2021 to January 2024.

2. List the criteria for exclusion

- Answer/Response: Subjects with ages <18 years

- Allergy to local anesthetic
- Inability to tolerate usual postoperative pain management regimen (Tylenol, Toradol, and Oxycodone PRN) for any reason
- Subjects who cannot read or understand English
- Subjects who are pregnant (self-reported)

3. List any restrictions on use of other drugs or treatments.

Answer/Response: None

Statistical Considerations

1. Is stratification/randomization involved?

Answer/Response: Yes

► IF YES, describe the stratification/ randomization scheme.

Answer/Response:

Random number generator will be used to enroll a subject into control TAP vs. Exparel TAP block group after consent is obtained before surgery. Patients will be blinded to their TAP block method. Surgeons/PI/ study coordinators will not be blinded to randomization. Surgeons/ PI/ study coordinators will have access to the randomization scheme.

► IF YES, who will generate the randomization scheme?

	Sponsor
	UVA Statistician.  Answer/Response:
	UVA Investigational Drug Service (IDS)
	Other:  Answer/Response: Study coordinator/ medical staff in plastic surgery clinic

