2. What are the statistical considerations for the protocol?

Answer/Response:

- This is a randomized, prospective trial that examines the effectiveness of Exparel TAP block (mix of Exparel + plain bupivacaine) compared to plain bupivacaine TAP block at University of Virginia Medical Center between February 2021 and January 2024. Patient information will be kept confidential and all identifying information will be removed. Data collected will involve:
 - General Demographic Data: age, gender, race, ethnicity, medical and surgical history, psychiatric history, medications, drug, smoking, alcohol abuse, occupation
 - Type of Reconstructive Procedure: procedure type, laterality

- TAP block information: liposomal bupivacaine vs. plain bupivacaine
- Post-operative Narcotic Requirement: total mg of oral opioid use in postop period during hospitalization and immediate post-operative period (30 days after discharge).
- Post-operative Data: LOS, pain scores, PONV incidence
- Complications

3. Provide a justification for the sample size used in this protocol.

Answer/Response: The primary outcome variable used for sample size calculation is post-operative narcotic requirement. Since we are unsure of the exact standard deviation for the population in terms of narcotic requirement, but we do have a limited number of patients that will be available for the study, we used four different standard deviations to confirm that we would have enough patients for 80% power ($\alpha = 0.05$) to detect a difference in groups. We believe that the estimate of the standard deviation is most likely in the 10 mg range, so having 50 patients in each group would allow us to detect a difference of 5.66 mg between groups at 80% power.

Sample sizes	Standard deviation	Alpha	Power	Difference that can be detected
50 50	1	0.05	80%	0.57 mg
50 50	5	0.05	80%	2.83 mg
50 50	10	0.05	80%	5.66 mg
50 50	15	0.05	80%	8.49 mg

4. What is your plan for primary variable analysis?

Answer/Response:

Univariate analysis with $\alpha < 0.05$ considered significant, variables with $p < 0.1$ will be included in multivariate analysis to control for potential confounding variables and attempt to determine independent factors associated with outcomes.

Primary outcomes will include post-op recovery data- pain scores and postop narcotic requirement (total mg of opioids) both during hospitalization and up to 30 days after discharge. Secondary outcomes will include LOS and incidence of PONV.

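### The opioid outcome that sizes the trial is oral-only in one item and has no stated route in another, with no common unit for different opioids

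*Combined protocol and SAP*

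**What the plan says.** All references are to the combined protocol and SAP.

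- **Sizing (Statistical Considerations, item 3).** "The primary outcome variable used for sample size calculation is post-operative narcotic requirement". On the spread: "We believe that the estimate of the standard deviation is most likely in the 10 mg range". The table gives detectable differences in plain mg and names no drug or equivalent.
- **Data collected (Statistical Considerations, item 2).** "Post-operative Narcotic Requirement: total mg of oral opioid use in postop period during hospitalization". The same entry goes on to cover the 30 days after discharge.
- **Primary analysis (Statistical Considerations, item 4).** "postop narcotic requirement (total mg of opioids", over the same two periods, with no route given.
- **Objectives/Hypothesis.** The outcome is listed separately for the hospital stay and for the period afterwards, for example "post-op narcotic pain medication use after discharge (within 30 days of discharge", with neither unit nor route.
- **Opioids mentioned.** One only, inside an exclusion criterion: "Inability to tolerate usual postoperative pain management regimen (Tylenol, Toradol, and Oxycodone PRN) for any reason".
- **Other drugs (Inclusion/Exclusion Criteria, item 3).** The answer to "List any restrictions on use of other drugs or treatments" is None.
- **Source (Human Participants, item 2).** "all the outcomes will be part of a usual post-op data that will be recorded in Epic".

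No section gives a reference opioid, an equivalence conversion or a rule for doses given by another route.

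**The concern.** A total in milligrams is a measure of opioid requirement only if every milligram counted means the same thing. That holds for one drug by one route. It fails once a second drug or a second route enters the sum, because a milligram of one opioid is not interchangeable with a milligram of another.

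The plan does not secure the single-drug case. It describes a usual regimen containing oxycodone but does not say that other opioids will not be used or will not be counted. For a patient whose chart holds a non-oral opioid, two analysts who follow items 2 and 4 literally could arrive at different totals. For a patient with two oral opioids of different strength, they could agree on a total that is hard to interpret.

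The surgeons, the investigator and the coordinators know the allocation (Statistical Considerations, item 1). If the choice of definition is left until the data are extracted, people who know the arms could be the ones to make it.

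**Working it through.** **1. Reproduce the plan's own figures.** Inputs from item 3: 50 per arm, alpha 0.05, power 80%, SD 1, 5, 10 or 15 mg. Neither the test nor its sidedness is stated; a two-sided two-sample t-test (98 degrees of freedom) reproduces the table. As a normal approximation, the detectable difference is (1.960 + 0.842) × SD × √(2/50) = 0.560 × SD. The noncentral t gives 0.5659 × SD.

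| SD (mg) | 0.5659 × SD | Plan |
|---|---|---|
| 1 | 0.57 | 0.57 |
| 5 | 2.83 | 2.83 |
| 10 | 5.66 | 5.66 |
| 15 | 8.49 | 8.49 |

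All four rows agree. A one-sided test does not fit (normal approximation: 4.97 mg at SD 10).

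**2. Write the candidate totals for one patient.** Let d_j be the mg of each drug-and-route combination j, and f_j its factor for conversion to a common unit.

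- Item 2, read literally: the sum of d_j over oral opioids only.
- Item 4, read literally and without conversion: the sum of d_j over all opioids.
- Common unit: the sum of f_j × d_j over all opioids.

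**3. Case A: oral oxycodone only.** The first two totals are identical. The third is the same total multiplied by one constant f. The difference and the SD both scale by f, so (f × 5.66)/(f × 10) = 0.566 and power stays at 80%. For example, an arbitrary f of 1.5 gives SD 15 and 8.49 mg, which is the table's fourth row.

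**4. Case B: some non-oral opioid.** The item 4 total minus the item 2 total is the patient's non-oral mg. The two group differences therefore disagree by the between-arm difference in mean non-oral mg, which is zero if such use is equal in the two arms. The SD can also change, because Var(oral + non-oral) = Var(oral) + Var(non-oral) + 2 Cov(oral, non-oral). The documents give none of these terms.

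**5. Case C: two oral opioids of different strength.** Items 2 and 4 agree, but both sum d_j with every f_j set equal unless a conversion is applied. The raw and converted totals are then not proportional across patients.

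**6. What cannot be computed.** The documents give no share of patients with non-oral or second-opioid use, no amounts, no split by arm and no conversion factors. No corrected difference, SD, power or sample size follows from them.

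**The case against.** The strongest reply is that item 4 merely abbreviates item 2. Both use the same label and the same two periods, item 2 carries the fuller description, and an analysis can use only what has been collected. This is plausible, and a reader who infers that the plan specifies two different outcomes goes further than the text allows. It does not close the gap, however. Item 2 alone still omits any non-oral opioid and still has no common unit for different oral opioids.

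The second reply is that the documents point to a single opioid: patients who cannot tolerate a regimen containing oxycodone are excluded, and no other opioid is named. That makes Case A a fair possibility, and the absence of restrictions on other drugs is not evidence that other opioids are used. But neither passage says that oxycodone is the only opioid, and its route is not given.

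The third reply is that item 4 is silent on conversion and does not prescribe a raw sum. That stands. The text supports only that unlike milligrams could be added under item 4, not that they would be.

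The fourth reply is that all opioids in morphine equivalents is a change to the item 2 outcome, whereas a clearly stated oral-only total would also align the two items. That is correct as far as the mismatch goes. An oral-only total would still leave out non-oral use and, without a conversion, would still count different oral opioids as equal.

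**Conclusion.** The point holds as a defect in the definition of the outcome that sizes the trial. The route differs between items 2 and 4, and neither item states a common unit. It deserves correction because the stated measure, followed literally, can omit or mis-weight opioid use, and because a better one is available at low cost.

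Its size is not known. If only oral oxycodone is used, there is no practical consequence. If other opioids or routes occur, individual totals depend on which wording is followed, and the group difference under items 2 and 4 disagrees only if non-oral use differs between arms. The documents neither show nor exclude that.

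Two stronger readings are tempting and are not supported. One is that the trial is underpowered or wrongly sized: the table is arithmetically correct, and a lower power appears only if one assumes a larger SD while holding the target at 5.66 mg, for which the documents give no basis. The other is that the comparison is biased: this would need a difference between arms in the use of other opioids, on which the documents give no information.

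**What to change.** Use one definition in items 2 and 4 of Statistical Considerations, for example: *total opioid use by any route, in mg of oral morphine equivalents, calculated from a conversion table fixed before any outcome data are extracted or viewed by arm*. The timing matters because the study team is not blinded; fixing the table only at data lock would be too late. The hospital and post-discharge totals can stay separate, as the Objectives already list them.

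In item 3, state that the planning SD and the detectable differences are in that unit.

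**Cost.** The Epic extract needs drug and route fields and a conversion step; this assumes that the record holds drug, dose and route. The totals will depend on the conversion table chosen. The planning SD must be re-expressed on the new scale, although the plan already says that it is uncertain. The detectable effect of 0.566 SD with 50 per arm does not change, and no extra patients or visits are needed.

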5. What is your plan for secondary variable analysis?

Answer/Response:

Secondary outcomes will include LOS and PONV.

Two-sample t-tests or Mann-Whitney U tests will be employed for secondary variable analysis.

Exploratory multivariate analysis will be employed to determine potential confounding variables and attempt to determine the focus for future studies to determine independent factors associated with various outcomes.

6. Have you been working with a statistician in designing this protocol?

Answer/Response: Yes

IF YES, what is their name?

Answer/Response: [name]

7. Will data from multiple sites be combined during analysis?

Answer/Response: No

Study Procedures-Biomedical Research

1. What will be done in this protocol?

Answer/Response:

Participants will either receive plain bupivacaine TAP block (control/ usual care) or Exparel TAP block mix (experimental/ mix of Exparel and plain bupivacaine). Post-op data will be recorded in Epic and will be analyzed.

All the subjects will be recruited in UVA plastic surgery clinic when qualifying patients come in for pre-operative visits.

2. If this protocol involves study treatment, explain how a subject will be transitioned from study treatment when they have completed their participation in the study.

Answer/Response: N/A

Subject Compliance with Study Procedures

1. Explain how the study team will monitor the subject for compliance with the study procedures.

(e.g. study team will administer study drug/ study interventions, study drug inventory of dispensed and returned drug, diary etc.)

Answer/Response: N/A

2. Describe criteria for when a subject is considered to be non-compliant with study procedures.

(e.g. subject returns more than 20% of the study drug, subject misses 20% of study visits)

Answer/Response: N/A

Bibliography

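### The primary analysis may yield two treatment results per outcome, one univariate and one from a p<0.1-screened model, without saying which decides or that randomized group stays in the model

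*Combined protocol and SAP*

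**What the plan says.** Item 4 of Statistical Considerations (primary variable analysis) gives the method in one sentence: "Univariate analysis with $\alpha < 0.05$ considered significant, variables with $p < 0.1$ will be included in multivariate analysis". The second step has two stated aims: control of confounding, and to "attempt to determine independent factors associated with outcomes". The item then lists the outcomes. It names no test, gives no list of candidate variables and makes no exception for randomized group.

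Three other places bear on it:

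- Objectives/Hypothesis lists several primary outcomes, beginning "Primary outcome = post-op pain scores during hospitalization, post-op narcotic pain medication use during hospitalization" and adding opioid use in the 30 days after discharge. The rule in item 4 thus applies three times.
- Item 3 (sample size) rests on a plain two-group difference: "having 50 patients in each group would allow us to detect a difference of 5.66 mg between groups at 80% power".
- Item 5 (secondary variable analysis) does name tests, but only for secondary outcomes: "Two-sample t-tests or Mann-Whitney U tests will be employed for secondary variable analysis". It adds: "Exploratory multivariate analysis will be employed to determine potential confounding variables".

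**The concern.** Randomization already deals with confounding in expectation. Choosing covariates by their p-values against the outcome is therefore not needed for that purpose. What it adds is a second treatment result whose model depends on the data.

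The main gap is that nothing says which result decides. If the two fall on opposite sides of 0.05, the plan has no rule to settle it. If either may be claimed, the error rate per outcome exceeds 5%. The surgeons, investigator and coordinators know the allocation, so a rule fixed in advance is worth more here than in a fully blinded trial.

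There are two smaller wording gaps. Item 4 does not state that randomized group is always in the model, and it does not limit covariates to those measured before the block.

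**Working it through.** **1. Which analysis does the sample size belong to?** Inputs from item 3: 50 per arm, SD 10 mg, alpha 0.05, power 80%.

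- Standard error of the difference = 10 × √(2/50) = 2.0 mg.
- Normal approximation, two-sided: 2.0 × (1.960 + 0.842) = 5.60 mg.
- Noncentral t, 98 df, two-sided: 5.659 mg, against 5.66 stated.
- The other rows (SD 1, 5, 15) give 0.566, 2.829 and 8.488 mg, against 0.57, 2.83 and 8.49.
- One-sided alpha gives 4.97 mg and does not match.

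The table is correct. It is the table of an unadjusted, two-sided, two-sample t-test.

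**2. If randomized group must itself pass p<0.1, how often is there no adjusted treatment estimate?** The noncentrality at 5.66 mg is 5.66 / 2.0 = 2.83.

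- P(p ≥ 0.1) at 5.66 mg, 98 df = 0.122.
- P(p ≥ 0.1) under no effect = 1 − 0.10 = 0.90.

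A trial with univariate p<0.05 always passes this screen, so no positive unadjusted result is lost.

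**3. Error rate and disagreement, by simulation.** The documents give neither a candidate list nor covariate strength, so these are assumptions: two baseline covariates that together explain 10% or 25% of outcome variance, plus 10 unrelated candidates, each screened at p<0.1 against the outcome. There were 40,000 runs under no effect and 20,000 at 5.66 mg. Paired entries are group screened / group always kept in.

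| Setting | Unadjusted p<0.05 | Multivariable p<0.05 | Either p<0.05 | Results disagree |
|---|---|---|---|---|
| No effect, 10% | 0.052 | 0.043 / 0.050 | 0.062 / 0.069 | – |
| No effect, 25% | 0.050 | 0.033 / 0.048 | 0.060 / 0.074 | – |
| 5.66 mg, 10% | 0.801 | 0.797 / 0.809 | – | 0.067 / 0.079 |
| 5.66 mg, 25% | 0.799 | 0.831 / 0.876 | – | 0.077 / 0.122 |

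Excess of either result over the unadjusted result in the same runs:

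- Group screened: 0.062 − 0.052 = 0.010 and 0.060 − 0.050 = 0.010.
- Group kept in: 0.069 − 0.052 = 0.017 and 0.074 − 0.050 = 0.024.

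**4. Sensitivity to the assumptions.**

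- With 3 to 20 unrelated candidates, the either-result rate is 5.6-6.2% (screened) and 6.4-7.4% (kept in).
- Separate runs under the same covariate assumptions put disagreement at 7-13%.
- With 12-20 covariates explaining 0-40% of variance and group kept in, the either-result rate is 5.9-7.9%. Disagreement at 5.66 mg, taken as P(either) − P(both), runs from 0.818 − 0.772 = 0.046 at 0% to 0.949 − 0.789 = 0.160 at 40%.
- At 0% explained, the screened multivariable result has power 0.781 against 0.807 unadjusted. At 10-25% it is 0.797-0.831 against about 0.80, so there the rule costs no power.

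**The case against.** The best case for the plan is that the univariate result is plainly the intended one. Item 4 attaches its only significance threshold to that step: "Univariate analysis with $\alpha < 0.05$ considered significant". Item 3 reproduces only as an unadjusted comparison. Item 5 describes similar multivariable work in almost the same terms and calls it exploratory. On this view the plan lacks one clarifying sentence, and the inflation depends on a freedom to claim either result that no passage grants.

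Much of this stands. The univariate reading is the more natural one, the harm is conditional, and its size depends on assumed covariates. But a sample-size method is not a decision rule. Item 4 gives confounder control for the primary outcomes to the second model, and the word exploratory appears only under secondary variable analysis. Either result could still be defended as primary once the data are seen.

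A reader might also infer three stronger points that the documents do not support:

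- **That two treatment results always arise.** Read literally, the second exists only when group itself reaches p<0.1.
- **That treatment will be dropped from the model, or that variables measured after the block will be used as covariates.** The text is silent on both; it plans neither.
- **That the screened model is itself an invalid test.** Its own error rate is 3.3-4.3% with group screened and 4.8-5.0% with group kept in.

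**Conclusion.** The gap is real and modest, and it should be fixed before analysis. The plan states a data-dependent second analysis for the primary outcomes and no rule for which treatment result counts.

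If either may be claimed, the error rate per outcome rises from 5% to about 6% (group screened) or 6.5-7.4% (group kept in), a net excess of about 1 to 2.5 percentage points. At the design difference the two results conflict in about 7-13% of trials. These figures rest on normal outcomes and on baseline covariates assumed to explain 10-25% of variance. The 12% and 90% rates of a missing adjusted estimate need no covariate assumption, but apply only if group is screened like any other variable.

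The finding does not dispute the sample-size table, does not say that the trial's error rate is inflated as written, and is separate from having three primary outcomes.

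**What to change.** Replace the rule in item 4 with wording such as:

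> For each primary outcome the deciding result is the unadjusted difference between randomized groups with its 95% CI (two-sample t-test, two-sided 0.05, matching the sample-size calculation). A Mann-Whitney U test is the sensitivity analysis for skewed opioid totals. Any adjusted analysis is supportive, always contains randomized group, and uses only covariates named in advance and measured before the block. Screening at p<0.1 for independent factors is exploratory.

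Move that screening to the exploratory analysis in item 5.

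The cost is SAP wording only: no new data and no loss of planned power. The downside is that an unadjusted deciding result gives up any precision that adjustment might bring.

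As an option, the team may name one pre-specified adjusted model as deciding instead, for example group plus laterality, which is already collected ("Type of Reconstructive Procedure: procedure type, laterality"). No passage says that laterality is prognostic, so this is the team's judgement. If it is not, power is about 0.80 with ordinary standard errors (0.798 against 0.802 for the t-test) or 0.79 with HC3 robust errors. How pain scores are summarised per patient is a separate matter and not part of this change.

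### The p<0.1 covariate rule for the primary outcomes does not exclude post-randomization variables, so an adjusted treatment estimate could be biased

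*Combined protocol and SAP*

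**What the plan says.** Statistical Considerations, question 4 (primary variable analysis), sets a univariate step judged at 0.05. It then says that variables with p below 0.1 "will be included in multivariate analysis to control for potential confounding variables and attempt to determine independent factors associated with outcomes". It names no candidate covariates, does not restrict them to baseline, and does not bar one outcome from the model of another. It does not say that arm stays in the model, or whether the univariate or the multivariate result decides.

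Question 2 of the same section holds the document's only list of variables. Demographics, history, medications, procedure type and laterality stand beside opioid totals, complications and this line: "Post-operative Data: LOS, pain scores, PONV incidence". Randomization takes place before surgery, so all the post-operative items are post-randomization.

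Pain scores and opioid use are both primary outcomes. The Background section hypothesizes that the Exparel block will help pain control and recovery.

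For the secondary outcomes, question 5 names two-sample tests and labels the modelling separately: "Exploratory multivariate analysis will be employed to determine potential confounding variables". Question 4 carries no such label.

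**The concern.** A confounder must precede treatment. A pain score taken after the block may be a consequence of it, and the trial's hypothesis is that it is. Oxycodone is given as needed, so pain and opioid use should be correlated, and pain would be expected to pass a p<0.1 screen in an opioid model. The same holds for opioid use in a pain model.

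Once pain is in the opioid model, the arm coefficient no longer estimates the total effect of the block on opioid use. If pain lies on the causal path, the part of the effect that runs through pain is removed. If pain and opioid use share an unmeasured cause, conditioning on pain can create an arm difference where none exists. Randomization does not protect against either problem, and keeping arm in the model does not cure it. At stake is whether an adjusted primary result could hide a real opioid reduction or suggest a false increase.

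**Working it through.** **1. The plan's own figure.** Question 3 states that "having 50 patients in each group" "would allow us to detect a difference of 5.66 mg between groups at 80% power", with an SD of 10 mg. Sidedness is not stated, so two-sided 0.05 is taken.

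- SE of the difference = 10 × √(2/50) = 2.00 mg.
- 5.66 / 2.00 = 2.83. Noncentral t with 98 df gives power 0.800, so the figure reproduces. One-sided 0.05 would give about 4.97 mg (normal approximation).
- The table therefore describes an unadjusted two-group comparison. In SD units the planned difference is 5.66 / 10 = 0.566.

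**2. Assumptions that are not in the documents.** The block lowers pain by s = 0.566 SD, the same standardized size as the planned opioid difference. The within-arm pain-opioid correlation r is 0.3, 0.5 or 0.7. Pain passes the screen and enters a linear model with arm.

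**3. Formulas** (reductions counted as positive).

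- Adjusted difference = total difference − r × 10 × s = total difference − 5.66r.
- Adjusted SE = 2.00 × √(1 − r²) × √(1 + s²/4). The last factor reflects the overlap of arm and pain: √(1 + 0.566²/4) = √1.080 = 1.039.
- Chance of significance: noncentral t with 97 df, critical value 1.985.

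**4. Case A: a true opioid reduction of 5.66 mg.**

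| r | Adjusted difference (mg) | Adjusted SE (mg) | Ratio | Power |
|---|---|---|---|---|
| 0.3 | 5.66 − 1.70 = 3.96 | 2.00 × 0.954 × 1.039 = 1.98 | 2.00 | 51% |
| 0.5 | 5.66 − 2.83 = 2.83 | 2.00 × 0.866 × 1.039 = 1.80 | 1.57 | 34% |
| 0.7 | 5.66 − 3.96 = 1.70 | 2.00 × 0.714 × 1.039 = 1.48 | 1.14 | 20% |

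**5. Case B: no effect on opioid use, and pain and opioid use linked only by an unmeasured shared cause.** The adjusted difference is 0 − 5.66r, an apparent increase in opioid use on Exparel.

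| r | False difference (mg) | Ratio to SE | False-positive rate |
|---|---|---|---|
| 0.3 | 1.70 | 0.86 | 13% |
| 0.5 | 2.83 | 1.57 | 34% |
| 0.7 | 3.96 | 2.67 | 75% |

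**6. Check by simulation.** The rule was applied literally: pain was added only when its univariate p was below 0.1 (50 per arm, 2,000 trials per setting).

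- At a shift of 0.566 SD, Case A gave 4.1, 2.8 and 1.7 mg with power 53%, 35% and 19%. Case B gave false-positive rates of 13%, 34% and 76%. Pain passed the screen in 90% to 100% of trials.
- Over shifts of 0.3 to 0.8 SD and the same correlations, the Case A estimate ran from 4.7 down to 0.1 mg and power from 68% down to 5%. The Case B false-positive rate ran from 7% to 94%.
- The unadjusted comparison kept 79% to 82% power in Case A and 4% to 6% type I error in Case B.
- When the block did not shift pain at all, adjustment did no harm (type I error 4.6%).

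**The case against.** The strongest reply is that the plan never says post-operative variables will be covariates. Question 4 speaks of potential confounders, which a consequence of treatment is not, and its next paragraph names pain, opioid use, length of stay and PONV as outcomes. Question 2 lists data to be collected and is not offered as a covariate list. A sensible analyst might screen baseline items only. This stands in part: a reader might infer that these variables are certain to enter the models, but the text only permits it. Still, the rule is worded as an instruction, and its second aim, finding independent factors associated with outcomes, invites post-operative predictors.

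Second, question 4 also plans a univariate analysis, which is unaffected, and the sample size rests on an unadjusted comparison. That is correct. The losses above reach the trial's conclusion only if the multivariate model decides, and question 4 leaves this open.

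Third, Case B needs its stated assumption. If pain itself drives opioid use, a block that lowers pain yet leaves total opioid use unchanged must have an offsetting direct effect. The adjusted coefficient would then estimate that direct effect and would not be a false positive. This stands, and Case B is limited accordingly.

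Fourth, question 5 already calls its multivariate work exploratory. That is right, and the point is confined to question 4.

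**Conclusion.** The concern holds as a gap in an operative rule. Question 4 does not exclude post-randomization variables, and literal use could bias an adjusted arm estimate. With a 0.566 SD pain shift and correlations of 0.3 to 0.7, a true 5.66 mg effect would appear as about 4.0 to 1.7 mg, with power of about 51% to 20% instead of 80%. Under the shared-cause assumption with no opioid effect, the false-positive rate would be about 13% to 75%. The shift and the correlations are assumptions. The 10 mg SD is the plan's own belief: "We believe that the estimate of the standard deviation is most likely in the 10 mg range".

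A reader might infer two stronger conclusions that the documents do not support:

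- **That every primary outcome would be biased.** Bias requires that the variable is treated as a candidate, that it passes the screen, and that treatment affects it. Only pain in an opioid model was calculated. There is no figure for length of stay, PONV, complications or the pain-score models.
- **That complications would serve as predictors and never be compared between arms.** The protocol lists them as collected and is silent on their analysis. Silence does not establish either claim.

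The sample-size table is not in error and does not depend on this point.

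**What to change.** Add to Statistical Considerations, question 4, wording such as:

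> Only variables fixed before randomization (for example age, medical, surgical and psychiatric history, pre-operative medications, smoking, planned procedure type and laterality) may enter a model that estimates the treatment effect. Treatment arm is always kept in that model. Pain scores, opioid use, length of stay, PONV and complications are outcomes and will not be covariates in it. Any model of predictors that uses post-operative variables is descriptive and gives no treatment estimate.

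Question 4 should also say whether the unadjusted or the adjusted comparison decides. With covariates held to baseline, or with the unadjusted comparison, the planned 80% power and 5% error stand.

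The cost is a few sentences and slightly less freedom in model building. No new data or patients are needed. The change should be made before outcome data are analysed.
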